8.2 Subgroup Definition and Parameterization

Not applicable.

9**General Specifications for Data Analyses**

The results of this study will be reported using summary tables, figures, and data listings, as appropriate. All data will be summarized by study intervention and/or scheduled time point, as applicable.

Listings

In the individual participant data listing all individual data will be listed as measured. Repeated and unscheduled measurements will be included in the listings. All listings will be sorted by subject ID and nominal time point, if not stated otherwise.

Tables and Descriptive Statistics

All safety data will be summarized by study intervention, as appropriate. All PK data will be summarized by study intervention and nominal time point. All individual data will be listed as measured in the individual participant data listing. Repeated and unscheduled measurements included in the listings will not be used for statistical analyses or summaries, unless the repeated measurement was performed due to unreliable values/technical reasons, e.g., clotted samples.

Unless otherwise specified, continuous variables will be summarized using descriptive statistics, i.e., the number of participants with non-missing values (n), the number of participants with missing values (nmiss), mean, standard deviation, median, 25th percentile (Q1) and 75th percentile (Q3), minimum, and maximum. If there are no missing values, the number of participants with missing values should be indicated by a 0. Mean, Median, Q1, Q3, Min, Max will have the same precision as the SDTM data (decimal places). SD will be presented with one decimal place more than the mean.

Qualitative variables will be summarized by frequency counts and percentages. Unless otherwise stated the calculation of proportions will be based on the number of participants of the analysis set of interest that received the respective study intervention for safety and PK summaries and for all other evaluations the analysis set of interest [N]. Therefore, counts of missing observations will be included in the denominator and presented as a separate category.

The following labels will be used for the study interventions in tables, listings, and figures, if not stated otherwise:

Treatment A: A single oral administration of 45 mg evobrutinib (TF2 formulation) Batch A
= **CCI** (reference)

Treatment B: A single oral administration of 45 mg evobrutinib (TF2 formulation) Batch B
= **CCI** (lower dissolution bound)

Treatment C: A single oral administration of 45 mg evobrutinib (TF2 formulation) Batch C
= **CCI** (upper dissolution bound)

Treatment D: A single oral administration of 45 mg evobrutinib (TF2 formulation) Batch D
=CC1 (hammer-milled)

All statistical analyses will be performed using SAS® Software version 9.4 or higher.

9.1 Definition of Baseline and Change from Baseline

If not otherwise specified, 'baseline' refers to the last scheduled measurement before first administration of study intervention in each respective period.

However, if a participant is missing the baseline collection, the previous non-missing evaluation could become the baseline value (e.g. from Screening). If no baseline or previous to baseline evaluations exist, then the baseline value will be treated as missing.

Absolute changes from baseline are defined as

$$\text{absolute change} = \text{visit value} - \text{baseline value}$$

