## Evobrutinib (M2951) Relative Bioavailability of Evobrutinib Tablet Batches

MS200527\_0131

Assessment	Screening	Treatment								SFU by phone	Comments	
		P1		P2		P3		P4				
Study Day(s)	-28 to -2	-1	1	2	3	4	5	6	7	8	15 ± 3	Approximate 48-hour washout between doses on Days 1, 3, 5, and 7.
Period-specific Day(s)	-28 to -2	-1	1	2	1	2	1	2	1	2		
Administration of study intervention			X		X		X		X			Washout period of 48 hours.
Physical examination	X	X							X			A full physical examination will be performed at Screening and before discharge on Day 8, and a brief physical examination will be performed on Day -1.
Vital signs	X	X	X		X		X		X	X		Vital signs will be assessed on the days of dosing (Day 1, 3, 5, and 7) at predose and at 2 hours postdose. At visits where assessment time points coincide with each other, the following sequence of activities will be followed: 12-lead ECG followed by vital signs within 30 minutes before the specified time point preceding the PK sampling, which will be performed at the specified time point.
Safety ECG	X	X	X		X		X		X	X		12-lead ECG will be performed on the days of dosing (Day 1, 3, 5, and 7) at predose and at 2 hours postdose. See Vital signs (row above) for assessments that coincide.
Clinical laboratory safety tests	X	X					X		X			On Day 5, tests will be performed predose. Blood samples for the clinical laboratory safety assessments will be collected in a fasted condition.
PK sampling			X	X	X	X	X	X	X	X		Plasma samples for PK analysis will be collected on the days of dosing (i.e., Days 1, 3, 5, and 7) at predose and 0.25, 0.5, 1.0, 1.5, 2.0, 2.5, 3.0, 4.0, 6.0, 8.0, 12.0, 16.0, and 24.0 hours postdose. See Vital signs (row above) for assessments that coincide.
Previous medication	X											
Concomitant medication monitoring	X	<=====>						X				
AE monitoring	X	<=====>						X				

AE=Adverse Event, Day = Study Day, ECG = Electrocardiogram, eGFR = estimated Glomerular Filtration Rate;FSH = Follicle stimulating hormone, P=Period, PK=Pharmacokinetics.

CONFIDENTIAL  
INFORMATION

10/60

Global Version ID: CCI

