### 9.4.2                Safety Analyses

In general, for the evaluation of safety parameters, the numerical values will be summarized descriptively (N, arithmetic mean, median, standard deviation, minimum and maximum values). Categorical variables will be presented in frequency tables by the number of observations and percentages.

Adverse Event counts and participants with AEs will be summarized for each treatment by system organ class and preferred term. In addition, AEs will be tabulated and listed per participant and analyzed by severity and relationship to study drug.

Participants who prematurely withdrew from the study or from treatment will be displayed in a by-participant listing and summarized by primary withdrawal reason for each treatment sequence.

Safety laboratory parameters will be listed for each participant including changes from baseline and flags for measurements outside the reference ranges, where applicable. Laboratory parameters (hematology and clinical chemistry) will be summarized by time point including both absolute values and changes from baseline.

Vital signs by participant, including changes from baseline, will be listed and summarized by treatment and time point using descriptive statistics. Electrocardiogram parameters and physical examination assessments will be listed for each participant.

All safety analyses will be performed on the Safety Analysis set (Section 9.3)

Endpoint	Statistical Analysis Methods
Primary	No primary safety endpoints
Secondary	
Nature, occurrence, and severity of TEAEs	The number and percentage of participants experiencing at least 1 TEAE will be summarized by treatment as well as the number of events. Tables by relationship to study drug and by severity will be generated. AEs will be coded using MedDRA terminology.
Absolute values and changes in safety laboratory tests	All laboratory data will be reported with SI units. Laboratory parameters will be summarized using descriptive statistics for absolute values, changes from baseline (predose for the respective period) and data listings of abnormalities.
Single 12-lead electrocardiograms (ECGs) (morphology and time intervals PR, QRS, RR, QT and QTcF)	ECG data will be summarized by changes from baseline (predose for the respective period) values by treatment using descriptive statistics. Clinical noteworthy ECG findings for individual participants will be listed and summarized as appropriate.

Endpoint	Statistical Analysis Methods

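### For vital signs and ECG, SAP 9.1 permits a missing predose baseline in Periods 2–4 to be replaced by the 2-hour post-dose value under the preceding batch

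*SAP*

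**What the plan says.** SAP 9.1 defines the default by period: "baseline' refers to the last scheduled measurement before first administration of study intervention in each respective period". It then gives a fallback: "if a participant is missing the baseline collection, the previous non-missing evaluation could become the baseline value (e.g. from Screening"). Baseline is treated as missing only if nothing earlier exists. Change is the visit value minus the baseline value.

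The protocol's Schedule of Activities (section 1.3) fixes when values exist. For vital signs, "Vital signs will be assessed on the days of dosing (Day 1, 3, 5, and 7) at predose and at 2 hours postdose"; for ECG, "12-lead ECG will be performed on the days of dosing (Day 1, 3, 5, and 7) at predose and at 2 hours postdose". Both are also marked at Screening, Day -1 and Day 8, and neither on Days 2, 4 or 6.

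Protocol 9.4.2 gives the intended analysis: "ECG data will be summarized by changes from baseline (predose for the respective period) values by treatment using descriptive statistics". It names the same period-predose baseline for vital signs and provides no fallback for either.

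Three other SAP sections bear on the point:
- Section 7 declares no change from the protocol's planned analyses.
- Section 9.4 assumes data are missing completely at random and says nothing will be done about missing values.
- Sections 15.4 and 15.5 summarise vital signs and ECG by treatment as baseline, value at each evaluation, and change.

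**The concern.** Looking back to the last available value is harmless when everything earlier is off drug. That holds for Period 1, and the SAP's only example (Screening) belongs there. In Periods 2–4 of this crossover the participant has already been dosed, and the latest earlier vital-sign or ECG evaluation was taken 2 hours after another batch. Used as a baseline, it has two consequences:
- A post-dose value under one batch appears in the baseline row for a different batch.
- The change column compares two on-treatment values at the same post-dose time, so any effect shared by the batches drops out of that participant's change and the preceding batch's effect enters with a minus sign.

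At stake are the vital-sign and ECG summaries (including QTcF) that serve the secondary safety objective. The wording also gives no criterion for when the fallback applies, so two programmers could follow the SAP and produce different tables.

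**Working it through.** The plan states no figure for this point. The check has three parts: which value the rule reaches, what that does to one change, and what it does to a batch mean.

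**1. Which value the rule reaches.** Scheduled vital-sign and ECG evaluations run, in order: Screening; Day -1; then predose and 2 h on each of Days 1, 3, 5 and 7; then Day 8 (protocol 1.3). SAP section 9 normally keeps unscheduled values out of summaries, so they would not usually intervene.

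| Missing predose | Previous scheduled evaluation | Status |
|---|---|---|
| Day 1 (Period 1) | Day -1 | off drug |
| Day 3 (Period 2) | Day 1, 2 h | preceding batch |
| Day 5 (Period 3) | Day 3, 2 h | preceding batch |
| Day 7 (Period 4) | Day 5, 2 h | preceding batch |

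If that 2-hour value is also missing, the rule reaches further back. In the sequences in protocol 6.3.1 (ABCD, BDAC, CADB, DCBA), each batch falls in Periods 2–4 in three of the four sequences and is preceded once by each other batch. No batch is spared.

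Laboratory tests differ. They have no 2-hour sample, and "On Day 5, tests will be performed predose"; if that sample is missing, the previous scheduled one is Day -1, before any dose. SAP 15.3 in any case summarises absolute laboratory values.

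**2. One affected change.** Let μ be the participant's predose level (taken as equal across periods, measurement noise ignored), d the current batch's 2-hour effect and d_prev the preceding batch's.

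- Intended: (μ + d) − μ = d.
- With the fallback: (μ + d) − (μ + d_prev) = d − d_prev.

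The documents give no effect sizes, so the ratio d_prev/d is an assumption:

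| d_prev/d | Reported change |
|---|---|
| 0.5 | 0.5d |
| 0.8 | 0.2d |
| 1.0 | 0 |
| 1.25 | −0.25d |

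**3. The batch mean.** Protocol 6.3.1 allows at most 7 participants in each of 4 sequences, so N is at most 4 × 7 = 28; the planned number is not visible. With m affected participants:

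mean change = [(N − m)d + m(d − d_prev)] / N

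With d_prev = d this is d(N − m)/N:

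| m (N = 28) | Share of d reported |
|---|---|
| 1 | 27/28 = 96.4% |
| 2 | 26/28 = 92.9% |
| 3 | 25/28 = 89.3% |
| 21 (every Period 2–4 predose for that batch) | 7/28 = 25% |

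One missing predose value thus costs 1/28 ≈ 3.6% of the mean change. For a purely hypothetical 10 ms QTcF rise common to all batches, the affected participant would show 0 ms and the batch mean would fall by 10/28 ≈ 0.36 ms.

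If the affected change is left missing instead, the mean over the remaining participants still estimates d under the SAP's missing-completely-at-random assumption.

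**The case against.** The case for leaving the text alone has real substance.

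- **The rule is permissive.** The SAP says the earlier value could become baseline, and its example is an off-drug value. A reader might infer that the SAP mandates a post-dose baseline; it does not. This stands, but nothing excludes the post-dose value either, and in Periods 2–4 Screening is the previous evaluation only if everything after it is missing.
- **The default agrees with the protocol.** Both documents use the period's own predose value, and the visible protocol text is silent on a missing one. It would be too strong to say that the SAP's baseline definition as a whole contradicts the protocol. The departure lies in the fallback alone, but it is not declared in SAP section 7 and does not sit with SAP 9.4.
- **Individual data survive.** SAP section 9 lists all values as measured. SAP 15.4 and 15.5 summarise each evaluation as well as change, and the investigator's ECG interpretation is tabulated without reference to baseline. Under protocol 7.1.2, ECG findings are reviewed at collection, not from the derived change. A reader might infer that a participant's safety signal would vanish; only the derived change and the baseline entry are wrong.
- **Missing predose values should be rare.** Participants are resident from Day -1 to Day 8, and SAP section 9 lets a repeat be used when the original failed for technical reasons. The rule could act on 3 × 28 = 84 of 4 × 28 = 112 period baselines, but that counts opportunities and is not an expected frequency. The documents give no missingness rate.

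**Conclusion.** The point holds as a minor defect confined to vital signs and ECG. As written, SAP 9.1 permits an on-treatment value under the preceding batch to serve as baseline in Periods 2–4. When that happens, the affected participant's change is d − d_prev instead of d, and the baseline summary contains a post-dose value. The fallback departs from protocol 9.4.2 and is inconsistent with SAP 9.4.

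A reader might infer that a batch's whole change from baseline is cancelled. The documents do not support that. Cancellation is exact only for the affected participant and period, and only if the two batches have equal 2-hour effects. The batch mean is diluted by about 3.6% per missing predose value, assuming N = 28 and equal effects; a smaller N would raise that share. A reported minimum or maximum change could also be wrong if the affected participant held it.

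The analyses concerned are descriptive and secondary. The primary AUC and Cmax comparisons do not use this baseline, and laboratory summaries are outside the mechanism.

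**What to change.** In SAP 9.1, replace the fallback with wording to this effect:

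*In Period 1, if the predose value is missing, the last non-missing value before the first study dose (Day -1 or Screening) is used as baseline. In Periods 2 to 4, a post-dose value from an earlier period is never used as baseline; if the period's predose value is missing, baseline and change from baseline for that period are missing.*

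Add a cross-reference in SAP 9.4 so that the Period 1 fallback is a stated exception to the no-imputation rule. Carrying the Day 1 predose value into later periods is not recommended, because it too would depart from the protocol's period-predose baseline.

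The cost is a short wording change and one programming condition, with no new data. The downside is that an occasional change value will be missing; the absolute values stay in the listings and summaries.

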9.2 Study Day / Study Intervention Day

Study day 1 for this study is defined as the start date of study intervention, the day before is Day - 1 (no Day 0 is defined). Study day is defined relative to Day 1.

9.3 Definition of Duration and 'Time Since' Variables

The following definitions and calculations of duration, as applicable, will be applied:

- Duration of AE (in days hh:mm) = end date and time - start date and time of the AE, if missing time for either the beginning or end then = end date - start date + 1; in case of multiple records for the same AE, the duration will be calculated over all these records
- Days hh:mm from dosing = start date and time of the event - date and time dose administration (for TEAEs), if missing time for either the dosing or event then days hh:mm from dosing = event start date - date of dose administration + 1
- Relative (Rel.) Day in period of AE = start date of the event - date of admin in period + 1 (for AEs on or after the day of dosing within a period)
- Rel. Day in study of AE = start date of the event - date of first admin + 1 (for AEs on or after the day of dosing)
- Rel. Day in study of AE = start date of the event - date of first admin (for events before the day of dosing of the study only)

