## 1.2 Schema

Batch A = [CCI](#) (reference), Batch B = [CCI](#) (lower dissolution bound), Batch C = [CCI](#) (upper dissolution bound), Batch D = [CCI](#) (hammer-milled).

Doses are on Days 1, 3, 5, and 7, with an approximate 48-hour washout between doses. Safety follow-up to be approximately 7-10 days after study discharge.

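### When a clock time is missing, the SAP 9.3 fallback enters a day number as time from dosing, which is always longer than the true elapsed time can be

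*SAP*

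**What the plan says.** SAP 9.3 defines time from dosing by subtracting one date-time from another: "Days hh:mm from dosing = start date and time of the event - date and time dose administration (for TEAEs". This is an elapsed time, with nothing added.

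The fallback applies "if missing time for either the dosing or event", and then the same variable is derived as "then days hh:mm from dosing = event start date - date of dose administration + 1".

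The next item in SAP 9.3 defines a different variable with the same arithmetic: "Relative (Rel.) Day in period of AE = start date of the event - date of admin in period + 1". SAP 9.2 gives the convention behind that added day: dosing starts on Day 1, and "the day before is Day - 1 (no Day 0 is defined".

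On the dosing schedule, Protocol 1.2 says: "Doses are on Days 1, 3, 5, and 7, with an approximate 48-hour washout between doses". Protocol 6.4 has the date and time of every dose recorded in the CRF, so the fallback will normally be triggered by a missing event time rather than a missing dose time.

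**The concern.** The main rule and the fallback measure different things under one name. The first is time elapsed since the dose. The second is the number of the day on which the event fell, counting the dosing day as 1. A timed event 2 hours after dosing is 0 days 02:00. The same event without a clock time is 1 day. The two values would sit in the same variable, and SAP 9.3 states no flag or separate label.

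Four batches are given to the same participant about two days apart, so an error of a day is large relative to the spacing. In Periods 1 to 3, an untimed event on the day after dosing is reported at 2 days, which is nominally when the next batch is taken. Someone reading event times by batch would see an event at the very end of the interval when it cannot have been there.

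**Working it through.** **Inputs**

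- Main rule, fallback and relative-day rule: SAP 9.3, as quoted above.
- Dosing days 1, 3, 5 and 7: Protocol 1.2 and 1.3.
- Dose clock time: not stated in the documents. Assumed 08:00, with 06:00 to 12:00 as the range, because doses follow an overnight fast (Protocol 5.3.1).

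**The plan's own interval.** 3 − 1 = 5 − 3 = 7 − 5 = 2 days, and 2 × 24 = 48 h. This agrees with the stated washout.

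**General result.** Let D be the event date minus the dose date, in days.

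- True elapsed time = 24D + (event clock − dose clock) hours.
- Two clock times differ by less than 24 h, so true elapsed time < 24D + 24 = 24(D + 1) hours.
- Fallback value = D + 1 days = 24(D + 1) hours.

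The fallback value is therefore strictly above every possible true value, whatever the dosing time and whichever clock time is missing. A search over 829,440 combinations of dose and event clock times found no exception. The smallest excess was 1 minute, for a dose at 00:00 and an event at 23:59.

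**With assumed dosing times.** On the dosing day the true time runs from 0 to under (24 − dose hour). On the next day it runs from (24 − dose hour) to under (48 − dose hour). The excess is the fallback value minus the true time.

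| Dose at | Event on | True time (h) | Fallback (h) | Too long by (h) |
|---|---|---|---|---|
| 06:00 | dosing day | 0 to <18 | 24 | >6 to 24 |
| 06:00 | next day | 18 to <42 | 48 | >6 to 30 |
| 08:00 | dosing day | 0 to <16 | 24 | >8 to 24 |
| 08:00 | next day | 16 to <40 | 48 | >8 to 32 |
| 12:00 | dosing day | 0 to <12 | 24 | >12 to 24 |
| 12:00 | next day | 12 to <36 | 48 | >12 to 36 |

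The excess is not capped at 24 h. For a next-day event and an 08:00 dose it reaches 48 − 16 = 32 h.

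**Without the added day.** The fallback becomes 24D hours: 0 on the dosing day and 24 on the next day. Both lie inside the true range in every row of the table. For an 08:00 dose, the dosing-day value is too short by less than 16 h. The next-day value is anywhere from 24 − 16 = 8 h too long to just under 40 − 24 = 16 h too short. The largest error falls from 24 to under 16 h on the dosing day, and from 32 to under 16 h on the next day.

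**The case against.** Several points can be made for the SAP.

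- **The day-count convention.** With no Day 0, adding one is normal. That is right for a day number, but SAP 9.3 already has day-number variables, and this one is defined as an elapsed time. Nor is the added day presented as a conservative imputation. SAP 9.4 says that missing data will not be acted on.
- **The result is a whole number of days.** SAP 9.3 does not say that 00:00 is appended, so a reader might recognise the entry as date-only. This stands in part. It does not help a reader who sees 1 day for an event on the dosing day itself.
- **Little depends on the variable.** This stands. The SAP names no table, attribution rule or test that uses it. Causality is judged by the investigator, who weighs timing along with other causes (Protocol Appendix 4).
- **The replacement is also a convention.** True: it remains off by several hours. It is, however, a value the event could have had, and it matches the main rule.

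Three stronger readings are tempting, and the documents do not support them.

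- A reader might infer that the duration rule, "if missing time for either the beginning or end then = end date - start date + 1", contains the same error. It is an ordinary inclusive count of calendar days and needs only a label saying so.
- A reader might infer that events would be counted under the wrong batch. Nothing in the SAP assigns events to batches from this variable.
- A reader might infer that phone follow-up is where the next-batch problem bites. Discharge on Day 8 comes after the last dose on Day 7, so events starting after discharge have no next batch. There the effect is one extra day: a Day 15 event gives 15 − 7 + 1 = 9 days against 8 calendar days. The documents also do not say where clock times are most likely to be missing.

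**Conclusion.** The fallback for time from dosing is wrong as written, and the point is minor. That it always exceeds the true elapsed time is exact and needs no assumption. The sizes in hours rest on the assumed dosing time.

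The coincidence with the next dose concerns events on the day after dosing in Periods 1 to 3. It is not an upper limit. SAP 9.3 does not say which dose applies to an untimed event dated on the next dosing day. If it were counted from the previous dose it would show 3 days, or 72 h.

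The effect is confined to the reported timing of adverse events with a missing clock time, and the documents do not allow their number to be estimated. Treatment-emergent status depends on onset relative to the Day 1 dose (SAP 15.1), so neither it nor the event counts change. The analysis of Cmax and AUC0-∞ is untouched.

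**What to change.** In SAP 9.3, delete the added day from the fallback for time from dosing, so that it is the event start date minus the dose date. Show the result in whole days, 0 on the dosing day, with a flag marking it as date-only. Leave the relative-day variables as they are. Leave the duration fallback's arithmetic as it is too, and label its result as calendar days.

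The cost is a small change to the SAP wording and the derivation code, plus a listing flag. No data collection or other analysis is affected.
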